**NCTo2540629**

**08/06/2015**

## Study protocol

### Study design and Setting

This study was a before and after study of the implementation of a bundle of UTIS CPR programs in Seoul Metropolitan City. The before phase was defined as January 2013 through December 2014 and included a historic control population. The after phase was defined as January 2015 through December 2016.

Seoul has approximately 10 million inhabitants per 605 km^2. The SMFD provides fire-based and public service under 24 EMS agencies with 140 ambulances with a single unified dispatch center, with approximately 300,000 transports per year including 4,800 OHCAAs. EMS providers can provide care comparable to an intermediate emergency medical technician (EMT-I) level in the United States. EMTs cannot declare death or stop CPR in the field unless a return of spontaneous circulation (ROSC) occurs. Therefore, all patients with OHCA are transported to emergency departments (EDs) while receiving CPR in an ambulance. The EMS CPR protocols were revised on the 2010 and 2015 International guidelines.

In Seoul, a DACPR program was implemented in 2010 and has been in effect for all calls suspected to involve cardiac arrest. The dispatch center has a standard protocol for DACPR with two steps; 1) screening potential OHCAAs by primary call dispatcher (PCD) and 2) providing telephone CPR instruction by medical call dispatcher (MCD). Prior to 2015, Seoul was covered by a single-tiered EMS service to respond to OHCA events. A nearest and available ambulance was dispatched to an OHCA event. Of the 140 ambulances, only 27 (23.3%) were equipped with a defibrillator with a feedback function until December 2014. However, there was no active feedback CPR training as a feedback to EMTs after review of the CPR records by medical directors.

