### Intervention

A bundle of three UTIS CPR programs were implemented in Jan. 2015; 1) a high-quality DACPR program, 2) a rapid dispatch program using MTR, and 3) an FCPR program using defibrillators with feedback functions. A high-quality DACPR program was implemented in 2015 in addition routine DACPR program. This program included monthly monitoring and evaluation of the quality of the call

receiving and consulting stages by a medical director. Ten percent of the calls correctly identified as cardiac arrest and 10% of the calls not recognized as cardiac arrest were randomly selected based on the records from the ambulance run sheet. The audit reviews were performed in a standardized manner and recorded on an audio review evaluation sheet. Performance standard indicators were set, and feedback for the executive members, including the dispatch center officers and medical directors during the study period. Key performance standard indicators included OHCA detection rate by the PCD and proportion of calls given CPR instructions within 120 seconds. Monthly education conferences for dispatchers were conducted to get feedback of the performance standards per individual and per dispatch teams. The rapid CPR program included a multi-tier response (MTR) using the nearest available fire engine or basic life support vehicle team in addition to routine ambulance dispatch. An MTR scene protocol was developed, and a train-the-trainer model was used to disseminate the protocol. Six education programs were conducted, and 141 (10.8% of all the EMS providers in Seoul) participants from 24 EMS agencies were trained as trainers in 2015. They conducted MTR CPR training programs for all the EMTs and firefighters in Seoul. The FCPR program included the distribution of defibrillators with feedback functions to each ambulance and EMT training program; EMS personnel were also strongly encouraged to use a defibrillator with a feedback function for professional recording of EMS-CPR, and the medical director provided feedback to the individual teams using these defibrillators. All CPR processes were recorded by these devices and uploaded by the EMTs after CPR to an electronic server of the SMFD to be reviewed by the EMS medical directors. The MTR was a newly implemented program, but the other two programs were incomplete before 2015. It is a new attempt in this study to try to apply both programs (DACP and FCPR) robustly and systematically to the whole city EMS.

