#### Variables and measurement

Bystander CPR was categorized into the following 3 groups: bystander CPR with dispatcher assistance group, bystander CPR without dispatcher assistance group, and no bystander CPR group. The MTR was positive if more than 2 vehicles arrived to cases with the same accident number. There were two types of MTR including an ambulance-tiered response (ATR) and a fire-engine-tiered response (FTR). FCPR was considered as positive if the corresponding ambulance used a defibrillator with feedback function. We collected following variables 1) demographics (age, gender, past medical history (diabetes mellitus, hypertension, heart disease, and stroke), event date and time (season, weekend, daytime)), 2)

community factors (location of arrest (public vs. private vs. other), witness status, primary cardiac rhythm at the scene (shockable, PEA and asystole), and bystander CPR or defibrillation), 3) EMS factors (EMS defibrillation, prehospital advanced airway, fluid resuscitation, mechanical CPR device use, detection time interval from call to detection of OHCA by the dispatcher, and EMS time intervals (response time interval, scene time interval, and transport time interval), and 4) post-resuscitative care (cardiac reperfusion therapy, targeted temperature management, and extracorporeal membrane oxygenation (ECMO)).

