#### Statistical analysis

The demographic findings and survival outcomes of the study population by study period are compared. The continuous variables were compared using the Wilcoxon rank sum test and the categorical variables were compared using the chi-squared test. The temporal trends by study period with six-month interval on performance indicators for each intervention were evaluated by the Cochran-Armitage test for the trends. We calculated the absolute differences (AD) with 95% confidence intervals (CIs) of the outcomes between the study periods and between the patient groups receiving each CPR program. A mixed-effects logistic regression model using the GLIMMIX procedure was used to estimate the association between the study period with outcomes, adjusting for the following: demographics (Model 1); demographics, community factors, and EMS factors (Model 2); demographics, community factors and EMS factors, and post-resuscitation care factors (Model 3); and finally, demographics, community factors and EMS factors, ACLS factors, and post-resuscitation care factors (Model 4). Outcomes were compared to assess the overall effect of all programs administered to patients before and after intervention. To assess the

individual effects of each program, a multi-variable logistic regression analysis was performed to evaluate the association between individual programs and outcomes. We constructed a mixed-effects logistic regression model to test the association between each CPR program (DACPR, MTR, and FCPR) and outcomes that was adjusted for potential confounders. We included random intercepts for ambulance station to control for clustering within the ambulance stations in both models. The effect sizes were calculated with AOR and 95% CIs. The p value was set at 0.05, and all statistical tests were 2-tailed. All statistical analyses were performed using the SAS version 9.4 software (SAS Institute Inc., Cary, NC, USA) and R version 3.4.1 (available at <https://www.rproject.org>. accessed on Feb. 25, 2018).

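### With only a station random intercept, the FCPR odds ratio may mix differences between stations with the effect of feedback CPR; a within-station estimate should be reported beside it

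*Combined protocol and SAP*

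**What the plan says.** The Statistical analysis section plans one model for the study period and another for the separate programs: "We constructed a mixed-effects logistic regression model to test the association between each CPR program (DACPR, MTR, and FCPR) and outcomes". The second is meant to show what each program does on its own. It is adjusted for confounders that are not listed, and study phase is not named among its covariates. The station term is the same in both: "We included random intercepts for ambulance station to control for clustering within the ambulance stations in both models". No station fixed effect, station-level mean of program use or within-station contrast is described.

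Three other statements fix how FCPR exposure arises:

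- Variables and measurement: "FCPR was considered as positive if the corresponding ambulance used a defibrillator with feedback function".
- Study design and Setting, for the before phase: "Of the 140 ambulances, only 27 (23.3%) were equipped with a defibrillator with a feedback function until December 2014".
- Intervention, for the after phase: "The FCPR program included the distribution of defibrillators with feedback functions to each ambulance and EMT training program", together with "EMS personnel were also strongly encouraged to use a defibrillator with a feedback function for professional recording of EMS-CPR".

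The documents do not say how the 27 ambulances were chosen, how FCPR use varied by station, how many stations there were, or how far outcomes differed between stations.

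**The concern.** A random-intercept logistic model draws on two kinds of contrast: patients with and without FCPR in the same station, and stations with more and less FCPR use. The second is free of station-level confounding only if the station effect is unrelated to how much the station used the program. The plan neither states nor checks that condition.

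For FCPR there is reason to doubt it. Before 2015 exposure depended on which ambulances held a device, and no random allocation is described. From 2015 it depended on whether crews used the device. The listed covariates describe patients, events, treatments and time intervals; none measures crew skill or CPR quality. If stations with better results also used the device more, a program with no effect would appear beneficial. This would shift the odds ratio itself, not just its interval.

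**Working it through.** **Documented inputs.** 4,035 patients per period, so 2 × 4,035 = 8,070; survival of 9% and 11% (Sample size calculation); 24 agencies and 140 ambulances, 27 with the device before 2015 (Study design and Setting). The plan prints no figure for this point to reproduce. Its device share does not reproduce (27/140 = 19.3%, not 23.3%; 27/0.233 is about 116), but that is a separate matter and does not affect this one.

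**Assumed inputs.** Station SD on the log-odds scale, correlation between a station's FCPR use and its effect on outcome, uptake after 2015, and number of stations.

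**Why the number of stations matters.** In a linear approximation, the between-station contrast keeps a fraction λ = 1 / (1 + n·σ²·p(1 − p)) of its full weight, where n is patients per station and σ the station SD. Take p = 0.10 (midway between 9% and 11%) and σ = 0.3, so σ²·p(1 − p) = 0.09 × 0.09 = 0.0081.

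- 140 stations: n = 8,070/140 = 57.6; λ = 1/(1 + 0.467) = 0.68.
- 24 stations: n = 8,070/24 = 336; λ = 1/(1 + 2.72) = 0.27.

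With many small stations, most of the between-station contrast gets through; with few large ones, most is removed.

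**Simulation.** Random-intercept logistic model fitted by maximum likelihood with Gauss-Hermite quadrature; true FCPR odds ratio 1.00; study phase in the model; fitted with and without the station mean of FCPR use. Percentages are two-sided 5% rejection rates.

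| Setting | Random intercept only | With station mean |
|---|---|---|
| 9,000 patients, 100 stations, SD 0.3, correlation 0.5 | 1.11 (21%) | 1.01 (4.7%) |
| Same, correlation 0.3 | 1.06 (8.7%) | 1.00 (5.7%) |
| 8,070 patients, 140 stations, SD 0.3, correlation 0.5 | 1.14 (33%) | 1.00 (4%) |
| 8,070, 140 stations, SD 0.2, correlation 0.5 / 0.8 | 1.11 / 1.19 | 1.00 / 1.01 |
| 8,070, 140 stations, SD 0.4, correlation 0.5 / 0.8 | 1.16 / 1.30 | 1.01 / 1.02 |
| 8,070, 24 stations, SD 0.2 to 0.4, correlation 0.5 to 0.8 | 1.01 to 1.04 | 0.98 to 0.99 |
| 8,070, 24 or 140 stations, correlation 0 | 0.99 to 1.01 | 0.99 to 1.01 |
| 14,000 patients, 5% events, SD 0.3, correlation 0.5; 140 / 100 / 60 / 24 stations | 1.14 / 1.13 / 1.11 / 1.06 | 1.00 to 1.01 |

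The 9,000-patient rows use 300 replicates; the 14,000-patient row and the 8,070-patient row at SD 0.3 use 150; the others use 60, with Monte Carlo SE of about 0.010 to 0.015 on the log scale. A further run at SD 0.3 and correlation 0.5 gave 1.13 to 1.14 with 100 to 140 stations, and about 1.02 with the station mean. In the 8,070-patient runs at SD 0.2 and 0.4, device holding before 2015 was all-or-nothing by station with 140 stations but graded with 24, so part of the fall between those rows comes from that choice.

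**Scale.** The planned 9% to 11% is an odds ratio of (0.11/0.89)/(0.09/0.91) = 1.25, log 0.223. An odds ratio of 1.11 to 1.14 has log 0.104 to 0.131, about 47 to 59% of that.

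**Precision.** In the first row the SE rises from 0.095 to 0.102, about 7%. Across the 14,000-patient runs the rise is about 2 to 10%.

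**Limits of the remedy.** If selection is by crew within station (SD 0.3, correlation 0.5, 9,000 patients, 40 replicates), the null odds ratio is 1.20 with 35 stations of 4 crews and still 1.18 with the station mean; with 24 units of 6 crews it goes from 1.19 to 1.17. A separate run went from 1.19 to 1.16. If the period has a log odds ratio of 0.22 and phase is left out, the null odds ratio is 1.23, and 1.14 with the station mean. Phase must therefore be in the model as well.

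**The case against.** The strongest reply is that nothing in the documents links FCPR use to station quality. The plan says only that 27 ambulances had the device. It does not say they were chosen for good performance, and from 2015 every ambulance was to receive one. With no correlation there is no bias. The size also turns on inputs the documents do not give: with 24 clusters the spurious odds ratio is near 1.04. All of this stands, and it is why the point is worded as what may happen. It does not remove the point, because the planned model needs zero correlation and the within-station estimate does not. In addition, 24 is the number of agencies, whereas the plan clusters on ambulance station.

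A second reply is that the device belongs to an ambulance and its use to a crew, so selection may operate inside stations, where a station mean hardly helps. This also stands, and it limits what the within-station estimate may be called.

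A reader might extend the argument to MTR. The documents do not support that: they describe dispatch of the closest free second vehicle, event by event, with no choice by station. At SD 0.4 and correlation 0.5 to 0.8 the MTR odds ratio was 1.08 to 1.15 with 140 clusters and 1.02 to 1.03 with 24, but that correlation has no footing in the text.

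Finally, the random intercept's stated purpose is clustering, and it serves that purpose. The bundle comparison of before with after is not affected by this point.

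**Conclusion.** The point holds for FCPR as a cheap improvement. The planned model leaves the FCPR odds ratio open to station-level confounding, and the way devices were held and used makes the needed independence doubtful. At station SD 0.3 and correlation 0.5, with phase in the model, a null effect would show as about 1.11 to 1.14 with 100 to 140 stations, about 1.04 with 24, and about 1.0 if the correlation is zero. Station SD, correlation, uptake and station count are assumptions.

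A reader might infer that better stations did receive or use the devices first, so that the FCPR result is known to be biased. No section shows that. Nor does the point show that a within-station odds ratio would be a clean program effect.

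**What to change.** In the FCPR model, include study phase and the station-level mean of FCPR use (the within-between, or Mundlak, form); station fixed effects are an alternative. Report the within-station odds ratio beside the planned random-intercept odds ratio, and state the number of stations. If the two differ, describe the FCPR result as an association. State that selection by crew within a station is not removed, so the within-station odds ratio should not be called the program effect without that caveat. The same term for MTR is optional.

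The cost is a few sentences in the analysis section, one covariate derived from data already held, and intervals about 2 to 10% wider for the added estimate. The planned estimate stays in the report.

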#### Data sources and collection

We used the Korean OHCA Registry of by the Korea Centers for Disease Control and Prevention (CDC), which captures all incident cases of OHCA in the Seoul, was retrieved from the following four sources: the EMS run sheets for basic ambulance operation information, the EMS CPR registry, the dispatcher CPR registry, and the hospital OHCA registry for hospital care and outcomes. The medical record reviewers from the Korea CDC extracted the recorded information on the cause of arrest, hospital care

and outcomes from approximately 700 hospitals. To ensure the quality of the medical record review process, a quality management committee of emergency physicians, epidemiologists, statistical experts, and medical record review experts analyzed the data every month while providing feedback to each medical record reviewer.

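### Study phase switches by calendar date for the whole city, but the period models have no term for non-seasonal month-to-month variation; if such variation exists, the confidence interval and p-value for the bundle effect are too optimistic

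*Combined protocol and SAP*

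**What the plan says.** The section Study design and Setting describes a city-wide before-and-after comparison, in these words: "This study was a before and after study of the implementation of a bundle of UTIS CPR programs in Seoul Metropolitan City". Both phases are calendar blocks. For the control block the plan says: "The before phase was defined as January 2013 through December 2014 and included a historic control population". For the block under the bundle, which follows without a gap, it says: "The after phase was defined as January 2015 through December 2016". The Intervention section gives January 2015 as the start of all three programs. There is one dispatch centre and no concurrent control.

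Under Statistical analysis, the bundle effect is estimated by mixed-effects logistic regression with study period as the exposure (Models 1 to 4), and the only random effect is this: "We included random intercepts for ambulance station to control for clustering within the ambulance stations in both models". Variables and measurement lists the calendar covariates among the demographics, so they enter all four models: "event date and time (season, weekend, daytime". The six-month trend tests concern performance indicators, not outcomes. Absolute differences between periods get 95% intervals with no clustering adjustment described. No month effect, time-clustered variance or time-series model for outcomes is mentioned.

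**The concern.** On any given date every patient in the city is in the same phase, so the period contrast compares 24 calendar months with 24 others. Patients in the same month can share influences that act city-wide and are not seasonal. A station intercept removes stable differences between stations. Phase changes within stations, on the same day for all of them, so this intercept carries nothing of a deviation that all stations share in one month. Season, weekend and daytime remove the average yearly, weekly and daily pattern, not the departure of a particular month from it.

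The model therefore treats patients in the same month as independent, given station and covariates. If they are not, a variance component that acts directly on the period contrast is left out of its standard error, and the stated two-sided 0.05 level is exceeded. This concerns precision. It could occur with no drift over time, and a linear trend term would not remove it.

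**Working it through.** **Inputs.** From Sample size calculation: survival 9% before and 11% after, 80% power, alpha 0.05, 4,035 per phase. From Study design and Setting: 24 months per phase and about 4,800 arrests per year before exclusions. Assumed, because the documents do not give them: the between-month SD τ on the logit scale, and a 6% rate to illustrate a primary outcome (CPC 1 or 2) that is rarer than survival.

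**Step 1: the plan's own figure.** The standard two-sided formula for 9% v 11% gives 3,531 per group, or 3,631 with continuity correction. Neither is 4,035. An unstated 10% loss allowance would match it (3,631 / 0.90 = 4,035), and 85% power without correction comes close (4,039). The figure is therefore not called wrong, and 4,035 is used below as the phase size.

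**Step 2: standard error.** With m patients per month and event rate p, the variance of the period log odds ratio is about 2/(24·m·p(1−p)) from patients plus 2τ²/24 from months. The planned model counts only the first part, so

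true SE / model SE = √(1 + τ²·m·p(1−p)), and type I error = 2[1 − Φ(1.96 / ratio)].

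Here m = 4,035 / 24 = 168, so m·p(1−p) is 168.1 × 0.0564 = 9.48 at 6% and 168.1 × 0.0819 = 13.77 at 9%.

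| τ (logit SD) | SD in points at 9% | SE ratio, 6% | Type I, 6% | SE ratio, 9% | Type I, 9% |
|---|---|---|---|---|---|
| 0 | 0 | 1.00 | 5.0% | 1.00 | 5.0% |
| 0.05 | 0.4 | 1.01 | 5.3% | 1.02 | 5.4% |
| 0.10 | 0.8 | 1.05 | 6.1% | 1.07 | 6.6% |
| 0.15 | 1.2 | 1.10 | 7.5% | 1.14 | 8.7% |
| 0.20 | 1.6 | 1.17 | 9.5% | 1.25 | 11.5% |

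**Step 3: simulation.** With 48 months, 24 clusters, a 10% rate and no true effect, an analysis stratified by cluster (a stand-in for the station-intercept model) rejected in 5.4, 5.4, 6.6, 9.2 and 11.8% of 4,000 runs for τ = 0, 0.05, 0.10, 0.15 and 0.20. A t-test on monthly rates stayed at 4.3 to 5.4%. A purely seasonal pattern gave 5.2% with the stratified analysis, since each phase covers two whole years.

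**Step 4: ceiling on volume.** 4,800 × 2 = 9,600 per phase, or 400 per month before exclusions. At 9%, m·p(1−p) = 32.76, and the type I error for τ = 0.05, 0.10, 0.15 and 0.20 is 6.0, 8.9, 13.7 and 19.7%.

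**Step 5: correlated months.** With first-order autoregressive month effects, a 9% rate and 168 per month, simulation (20,000 runs) gives about:

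| τ | Correlation of adjacent months | Patient-level test | Month-level t-test |
|---|---|---|---|
| 0.10 | 0.3 | 8% | 6% |
| 0.10 | 0.6 | 11% | 9% |
| 0.15 | 0.3 | 12% | 7% |
| 0.15 | 0.6 | 17.5% | 12% |

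**Step 6: power.** For 9% v 11% with 4,035 per phase, SE = √(0.1798/4,035 + 2σ²/24), with σ = 0.09τ in proportion units. A month-level t-test on 46 df has power of about 83, 82, 78, 72 and 64% for τ = 0, 0.05, 0.10, 0.15 and 0.20.

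**The case against.** The strongest reply is that nothing in the documents shows the month variance to be above zero. That stands. A reader might infer that the planned intervals are known to be too narrow, but the documents support only a conditional statement. At τ = 0.05 the effect is negligible. Season is adjusted and balanced over whole years, and the rhythm, witness and EMS covariates of Models 2 to 4 may carry some of any shared variation.

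A reader might also take the monthly cycles in the text as evidence of clustering by month. They are weak evidence. The statement "Monthly education conferences for dispatchers were conducted" describes part of the 2015 program and says nothing about the before months. The registry committee "analyzed the data every month while providing feedback to each medical record reviewer", but nothing ties the month of record review to the month of the arrest.

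The 9% rate is for survival, the secondary outcome, so the 6% column is nearer the primary outcome, though 6% is itself an assumption.

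It is also tempting to read a month-level analysis as restoring 5% in general. Step 5 shows that it does so only when months are independent. Nor was the crossed mixed model itself simulated. At τ = 0.10, observed month-to-month variance was at or below the binomial level in about 29% of runs at a 9% rate and 36% at 6%, so an estimate of zero would not show that the variance is absent.

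Finally, with one switch date and no concurrent control, secular trend is arguably the larger threat. That is a separate matter of bias.

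**Conclusion.** The gap is real but its effect is conditional. Exposure is set by date alone, and no planned term carries non-seasonal variation shared across the city. Any such variation makes the interval and p-value for the period odds ratio and absolute difference too optimistic. The direction is certain if the variance is positive; the size cannot be derived from the documents. Over the assumed range of SD 0.05 to 0.20, with independent months and 168 patients per month, a nominal 5% test has a true level of about 5.3 to 9.5% at a 6% rate and 5.4 to 11.5% at 9%. More patients per month or positive correlation between months raises it; zero variance leaves it unchanged.

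The point concerns the period models and the period absolute differences. The sentence on station intercepts also covers the individual-program models, where exposure differs between patients in the same month and the problem is weaker.

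**What to change.** For the period models only:

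- Add a random intercept for calendar month of the event (48 levels), crossed with the station intercept. Keep season as a fixed covariate.
- Test study period on the between-month degrees of freedom, about 48 − 2 = 46, and state this in advance.
- Compute the interval for the period absolute difference with month as the cluster.
- Report the estimated month variance, including an estimate of zero.
- Check residual correlation between months. If it is present, use a serially correlated month effect (for example AR(1)) or a longer time block, because independent month intercepts remove only part of the inflation.

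The cost is modest. Event date is already collected and GLIMMIX is already the planned procedure, but the degrees of freedom, the clustered interval and the correlation check each need a sentence in the plan. If monthly variation exists, the interval widens and power falls as in step 6. The change corrects precision only. Bias from a secular trend needs its own remedy, and a month intercept should not be presented as providing it.
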